9.1.6. Case Report Forms

For each subject consented, an eCRF casebook will be completed by an authorized study staff member whose training for this function is completed in EDC. The eCRF casebook will only capture the data required per the protocol schedule of events and procedures. The Inclusion/Exclusion Criteria and Enrollment eCRFs should be completed only after all data related to eligibility have been received. Subsequent to data entry, a study monitor will perform

source data verification within the EDC system. System-generated or manual queries will be issued to the investigative site staff as data discrepancies are identified by the monitor or internal Gilead staff, who routinely review the data for completeness, correctness, and consistency. The site coordinator is responsible for responding to the queries in a timely manner, within the system, either by confirming the data as correct or updating the original entry, and providing the reason for the update (e.g. data entry error). Original entries as well as any changes to data fields will be stored in the audit trail of the system. Prior to any interim time points or database lock (as instructed by Gilead), the investigator will use his/her log in credentials to confirm that the forms have been reviewed, and that the entries accurately reflect the information in the source documents. At the conclusion of the trial, Gilead will provide the site with a read-only archive copy of the data entered by that site. This archive must be stored in accordance with the records retention requirements outlined in Section 9.1.5.

9.1.7. Investigational Medicinal Product Accountability and Return

Where possible, IMP should be destroyed at the site. If the site does not have acceptable procedures in place for drug destruction, arrangements will be made between the site and Gilead Sciences (or Gilead Sciences' representative) for return of used and unused IMP supplies.

The study monitor will provide instructions for return.

The study monitor will evaluate each study center's study drug disposal procedures and provide appropriate instruction for destruction of unused IMP supplies. If the site has an appropriate standard operating procedure (SOP) for drug destruction as determined by Gilead, the site may destroy used (empty or partially empty) and unused IMP supplies in accordance with that site's approved SOP. A copy of the site's approved SOP will be obtained for central files.

If IMP is destroyed on site, the investigator must maintain accurate records for all IMP destroyed. Records must show the identification and quantity of each unit destroyed, the method of destruction, and the person who disposed of the IMP. Upon study completion, copies of the IMP accountability records must be filed at the site. Another copy will be returned to Gilead. Refer to the Pharmacy Binder for study drug disposal/return instructions.

The study monitor will review IMP supplies and associated records at periodic intervals.

9.1.8. Inspections

The Investigator will make available all source documents and other records for this trial to Gilead's appointed study monitors, to IRB/IEC, or to regulatory authority or health authority inspectors.

9.1.9. Protocol Compliance

The investigator is responsible for ensuring the study is conducted in accordance with the procedures and evaluations described in this protocol.

9.2. Sponsor Responsibilities

9.2.1. Protocol Modifications

Protocol modifications, except those intended to reduce immediate risk to study subjects, may be made only by Gilead. The investigator must submit all protocol modifications to the IRB/IECs in accordance with local requirements and receive documented IRB/IECs approval before modifications can be implemented.

9.2.2. Study Report and Publications

A clinical study report (CSR) will be prepared and provided to the regulatory agency. Gilead will ensure that the report meets the standards set out in the ICH Guideline for Structure and Content of Clinical Study Reports (ICH E3). Note that an abbreviated report may be prepared in certain cases.

Investigators in this study may communicate, orally present, or publish in scientific journals or other scholarly media only after the following conditions have been met:

The results of the study in their entirety have been publicly disclosed by or with the consent of Gilead in an abstract, manuscript, or presentation form or the study has been completed at all study sites for at least 2 years.

The investigator will submit to Gilead any proposed publication or presentation along with the respective scientific journal or presentation forum at least 30 days before submission of the publication or presentation.

No such communication, presentation, or publication will include Gilead's confidential information (see Section [9.1.4](#)).

The investigator will comply with Gilead's request to delete references to its confidential information (other than the study results) in any paper or presentation and agrees to withhold publication or presentation for an additional 60 days in order to obtain patent protection if deemed necessary.

9.3. Joint Investigator/Sponsor Responsibilities

9.3.1. Payment Reporting

Investigators and their study staff may be asked to provide services performed under this protocol, e.g. attendance at Investigator's Meetings. If required under the applicable statutory and regulatory requirements, Gilead will capture and disclose to Federal and State agencies any expenses paid or reimbursed for such services, including any clinical trial payments, meal, travel expenses or reimbursements, consulting fees, and any other transfer of value.

9.3.2. Access to Information for Monitoring

In accordance with regulations and guidelines, the study monitor must have direct access to the investigator's source documentation in order to verify the accuracy of the data recorded in the CRF/eCRF.

The monitor is responsible for routine review of the CRF/eCRF at regular intervals throughout the study to verify adherence to the protocol and the completeness, consistency, and accuracy of the data being entered on them. The monitor should have access to any subject records needed to verify the entries on the CRF/eCRF. The investigator agrees to cooperate with the monitor to ensure that any problems detected through any type of monitoring (central, on site) are resolved.

9.3.3. Access to Information for Auditing or Inspections

Representatives of regulatory authorities or of Gilead may conduct inspections or audits of the clinical study. If the investigator is notified of an inspection by a regulatory authority the investigator agrees to notify the Gilead medical monitor immediately. The investigator agrees to provide to representatives of a regulatory agency or Gilead access to records, facilities, and personnel for the effective conduct of any inspection or audit.

9.3.4. Study Discontinuation

Both the sponsor and the investigator reserve the right to terminate the study at any time. Should this be necessary, both parties will arrange discontinuation procedures and notify the appropriate regulatory authority(ies), IRBs, and IECs. In terminating the study, Gilead and the investigator will assure that adequate consideration is given to the protection of the subjects' interests.

Appendix 2. Study Procedures Table

Appendix Table 1. Screening/Baseline/ On-Treatment and Post Treatment Study Visits for Group 1

	Screen	Baseline/Day 1 ^a	On-Treatment Week (± 3 Days)				Post-Treatment Week (± 5 Days)		
			2	4	6	8/ET	4	12	24
Informed Consent	X								
Determine Eligibility	X	X							
Medical History	X								
Physical Examination	X	X				X	X	X	X
Height	X								
Weight	X	X				X			
Vital Signs	X	X	X	X	X	X	X	X	X
12-Lead ECG	X	X				X			
AEs/SAE ^b	X	X	X	X	X	X	X	X ^b	X ^b
Concomitant Medications	X	X	X	X	X	X	X		
Pregnancy Prevention Counseling	X	X		X		X	X		
Health-Related Quality of Life ^c		X				X		X	
Review of Study Medication Compliance			X	X	X	X			
Study Drug Dispensing ^d		X		X					
Hematology, Chemistry	X	X	X	X	X	X	X	X	X
Coagulation Tests	X	X				X			
HCV RNA	X	X	X	X	X	X	X	X	X
Viral Sequencing/Phenotyping ^e		X	X	X	X	X	X	X	X
Sparse PK			X	X	X	X			
Intensive PK ^{g, h}					X ^h	X ^h			

	Screen	Baseline/Day 1 ^a	On-Treatment Week (± 3 Days)				Post-Treatment Week (± 5 Days)		
			2	4	6	8/ET	4	12	24
Hemodialysis PK ^{g,i}					X ⁱ	X ⁱ			
Serum β -hCG Pregnancy Test ^j	X	X		X		X	X		
Serum Drug Screen	X								
HCV & IL28B Genotyping	X								
HCV, HIV, HBV Serology	X								
HBV DNA ^k		X		X		X	X	X	X
HbA1c	X								
Fibrotest [®]	X								
Archive Sample ^f		X				X			
Pharmacogenomic Sample ^f		X							
CD4 Cell Count ^l	X	X		X		X	X		
HIV-1 RNA ^l	X	X		X		X	X		

a Baseline/Day 1 assessments must be performed prior to dosing

b Only SAEs will be collected at post-treatment Weeks 12 and 24.

c Health Related Quality of Life (HRQoL) Surveys (e.g., SF-36, CLDQ-HCV, FACIT-F and WPAI) will be conducted for all subjects where the surveys are available at Day 1, Week 8, ET (if applicable), and posttreatment Week 12.

d The IWRS will provide direction on the specifics of each subject's study drug dispensing

e. Plasma samples will be collected for possible viral resistance testing and other virology studies

f Subjects may opt out of archive/pharmacogenomics sample collection.

g Only for subjects who have provided consent for this sample and testing.

h Intensive PK evaluations will be assessed at the following timepoints: 0 (pre-dose -5 minutes), 0.25, 0.5, 1, 2, 4, 6 ,8, 10, and 12 hours post dose once either on Week 6 or 8, per investigator discretion.

i Hemodialysis PK blood samples will be collected at one hemodialysis session between Week 6 and Week 12, inclusive (as appropriate based on treatment group), evaluations will include: 1. A single blood sample will be collected within 10 minutes before hemodialysis initiates. 2. During hemodialysis, a single sample will be collected from both the arterial and venous sides of the dialyzer within 1 hour of hemodialysis concluding. 3. Finally, a single blood sample will be collected within 10 minutes after hemodialysis concludes.

j For females of child bearing potential only

k. Only for subjects who are HBcAb+ at Screening

l For HIV/HCV co-infected subjects only.

Appendix Table 2. Screening/Baseline/ On-Treatment and Post Treatment Study Visits for Group 2

	Screen	Baseline/Day1 ^a	On-Treatment Week (±3 Days)					Post-Treatment Week (±5 Days)		
			2	4	6	8	12/ET	4	12	24
Informed Consent	X									
Determine Eligibility	X	X								
Medical History	X									
Physical Examination	X	X					X	X	X	X
Height	X									
Weight	X	X					X			
Vital Signs	X	X	X	X	X	X	X	X	X	X
12-Lead ECG	X	X					X			
AEs/SAE ^b	X	X	X	X	X	X	X	X	X ^b	X ^b
Concomitant Medications	X	X	X	X	X	X	X	X		
Pregnancy Prevention Counseling	X	X		X		X	X	X		
Health-Related Quality of Life ^c		X					X		X	
Review of Study Medication Compliance			X	X	X	X	X			
Study Drug Dispensing ^d		X		X		X				
Hematology, Chemistry	X	X	X	X	X	X	X	X	X	X
Coagulation Tests	X	X					X			
HCV RNA	X	X	X	X	X	X	X	X	X	X
Viral Sequencing/Phenotyping ^e		X	X	X	X	X	X	X	X	X
Sparse PK			X	X	X	X	X			
Intensive PK ^{g, h}					X ^h	X ^h	X ^h			
Hemodialysis PK ^{g, i}					X ⁱ	X ⁱ	X ⁱ			

	Screen	Baseline/Day 1 ^a	On-Treatment Week (± 3 Days)					Post-Treatment Week (± 5 Days)		
			2	4	6	8	12/ET	4	12	24
Serum β -hCG Pregnancy Test ^j	X	X		X		X	X	X		
Serum Drug Screen	X									
HCV & IL28B Genotyping	X									
HCV, HIV, HBV Serology	X									
HBV DNA ^k		X		X		X	X	X	X	X
HbA1c	X									
Fibrotest [®]	X									
Archive Sample ^f		X					X			
Pharmacogenomic Sample ^f		X								
CD4 Cell Count ^l	X	X		X		X	X	X		
HIV-1 RNA ^l	X	X		X		X	X	X		

a Baseline/Day 1 assessments must be performed prior to dosing

b Only SAEs will be collected at post-treatment Weeks 12 and 24.

c Health Related Quality of Life (HRQoL) Surveys (e.g., SF-36, CLDQ-HCV, FACIT-F and WPAI) will be conducted for all subjects where the surveys are available at Day 1, Week 12, ET (if applicable), and posttreatment Week 12.

d The IWRS will provide direction on the specifics of each subject's study drug dispensing

e Plasma samples will be collected for possible viral resistance testing and other virology studies

f Subjects may opt out of archive/pharmacogenomics sample collection.

g Only for subjects who have provided consent for this sample and testing.

h Intensive PK evaluations will be assessed at the following timepoints: 0 (pre-dose -5 minutes), 0.25, 0.5, 1, 2, 4, 6, 8, 10, and 12 hours post dose once either on Week 6, 8, or 12 per investigator discretion.

i Hemodialysis PK blood samples will be collected at one hemodialysis session between Week 6 and Week 12, inclusive (as appropriate based on treatment regimen), evaluations will include: 1. A single blood sample will be collected within 10 minutes before hemodialysis initiates. 2. During hemodialysis, a single sample will be collected from both the arterial and venous sides of the dialyzer within 1 hour of hemodialysis concluding. 3. Finally, a single blood sample will be collected within 10 minutes after hemodialysis concludes.

j For females of child bearing potential

k Only for subjects who are HBcAb+ at Screening

l For HIV/HCV co-infected subjects only.

Appendix Table 3. Screening/Baseline/ On-Treatment and Post Treatment Study Visits for Group 3

	Screen	Baseline/Day1 ^a	On-Treatment Week (± 3 Days)								Post-Treatment Week (± 5 Days)		
			2	4	6	8	12	16	20	24/ET	4	12	24
Informed Consent	X												
Determine Eligibility	X	X											
Medical History	X												
Physical Examination	X	X									X	X	X
Height	X												
Weight	X	X									X		
Vital Signs	X	X	X	X	X	X	X	X	X	X	X	X	X
12-Lead ECG	X	X									X		
AEs/SAE ^b	X	X	X	X	X	X	X	X	X	X	X	X ^b	X ^b
Concomitant Medications	X	X	X	X	X	X	X	X	X	X	X		
Pregnancy Prevention Counseling	X	X		X		X	X	X	X	X	X		
Health-Related Quality of Life ^c		X									X		X
Review of Study Medication Compliance			X	X	X	X	X	X	X	X			
Study Drug Dispensing ^d		X		X		X	X	X	X				
Hematology, Chemistry	X	X	X	X	X	X	X	X	X	X	X	X	X
Coagulation Tests	X	X									X		
HCV RNA	X	X	X	X	X	X	X	X	X	X	X	X	X
Viral Sequencing/ Phenotyping ^e		X	X	X	X	X	X	X	X	X	X	X	X
Sparse PK			X	X	X	X	X	X	X	X			
Intensive PK ^{g, h}					X ^h	X ^h	X ^h						
Hemodialysis PK ^{g, i}					X ⁱ	X ⁱ	X ⁱ						

	Screen	Baseline/Day1 ^a	On-Treatment Week (± 3 Days)								Post-Treatment Week (± 5 Days)		
			2	4	6	8	12	16	20	24/ET	4	12	24
Serum β -hCG Pregnancy Test ^j	X	X		X		X	X	X	X	X	X		
Serum Drug Screen	X												
HCV & IL28B Genotyping	X												
HCV, HIV, HBV Serology	X												
HBV DNA ^k		X		X		X	X	X	X	X	X	X	X
HbA1c	X												
Fibrotest [®]	X												
Archive Sample ^f		X								X			
Pharmacogenomic Sample ^f		X											
CD4 Cell Count ^l	X	X		X		X	X	X	X	X	X		
HIV-1 RNA ^l	X	X		X		X	X	X	X	X	X		

a Baseline/Day 1 assessments must be performed prior to dosing

b Only SAEs will be collected at post-treatment Weeks 12 and 24.

c Health Related Quality of Life (HRQoL) Surveys (e.g., SF-36, CLDQ-HCV, FACIT-F and WPAI) will be conducted for all subjects where the surveys are available at Day 1, Week 24, ET (if applicable), and posttreatment Week 12.

d The IWRS will provide direction on the specifics of each subject's study drug dispensing

e Plasma samples will be collected for possible viral resistance testing and other virology studies

f Subjects may opt out of archive/pharmacogenomics sample collection.

g Only for subjects who have provided consent for this sample and testing.

h Intensive PK evaluations will be assessed at the following timepoints: 0 (pre-dose -5 minutes), 0.25, 0.5, 1, 2, 4, 6, 8, 10, and 12 hours post dose once either on Week 6-8, or 12 per investigator discretion.

i Hemodialysis PK blood samples will be collected at one hemodialysis session between Week 6 and Week 12, inclusive (as appropriate based on treatment regimen), evaluations will include: 1. A single blood sample will be collected within 10 minutes before hemodialysis initiates. 2. During hemodialysis, a single sample will be collected from both the arterial and venous sides of the dialyzer within 1 hour of hemodialysis concluding. 3. Finally a single blood sample will be collected within 10 minutes after hemodialysis concludes.

j For females of child bearing potential

k Only for subjects who are HBcAb+ at Screening

l For HIV/HCV co-infected subjects only.

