5.4. Prior and Concomitant Medications

Concomitant medications taken within 30 days prior to screening, up to and including 30 days after the last dose of study drug, need to be recorded in the source documents and electronic case report form(s) (eCRFs).

The following medications are prohibited during the screening period and for a minimum of **28 days prior to the Day 1** visit through the end of treatment:

- Granulocyte colony stimulating factors (GCSF) and thrombopoietin (TPO) mimetics
- Investigational agents or devices for any indication
- Chronic use of systemic immunosuppressants including, but not limited to, corticosteroids (prednisone equivalent of > 10 mg/day for > 2 weeks), azathioprine, or monoclonal antibodies (e.g., infliximab).

Concomitant use of certain medications or herbal/natural supplements (inhibitors or inducers of drug transporters, i.e., BCRP and P-gp) with study drug may result in PK interactions resulting in increases or decreases in exposure of study drug.

The use of amiodarone is prohibited from **60 days prior to Day 1** through the end of treatment; other examples of representative medications which are prohibited or are to be used with caution from **21 days prior to Day 1** through the end of treatment are listed below in [Table 5-1](#).

Table 5-1. Disallowed and Concomitant Medications to be Used with Caution

Drug Class	Agents Disallowed	Use with Caution
Acid Reducing Agents ^a		Proton-Pump Inhibitors, H2-Receptor Antagonists, Antacids
Anticonvulsants ^b	Phenobarbital, Phenytoin, Carbamazepine, Oxcarbazepine	
Antimycobacterials ^b	Rifabutin, Rifapentine, Rifampin	
Cardiac Medications	Amiodarone ^c	Digoxin ^d
Herbal/Natural Supplements ^b	St. John's Wort, Echinacea, Milk thistle (i.e., silymarin), Chinese herb sho-saiko-to (or Xiao-Shai-Hu-Tang)	
HMG-CoA Reductase Inhibitors ^e	Rosuvastatin	

a It is recommended to separate antacid and LDV/SOF administration by 4 hours. H2-receptor antagonists may be administered simultaneously with or staggered from LDV/SOF at a dose that does not exceed doses comparable to famotidine 40 mg twice daily. Proton-pump inhibitor doses comparable to omeprazole 20 mg can be administered simultaneously with LDV/SOF. Proton-pump inhibitors should not be taken before LDV/SOF.

b May result in a decrease in the concentrations of study drug.

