6.4. Post-treatment Assessments

6.4.1. Posttreatment Week 4 Visit (\pm 5 days): Group 1, Group 2, and Group 3

The following procedures/assessments are to be completed at Posttreatment Week 4:

- Perform complete physical examination, including vital signs
- Assessment of AEs and concomitant medications
- Pregnancy prevention counselling
- Subject completes Health Related Quality of Life Questionnaire: SF-36, CLDQ-HCV, FACIT-F, and WPAI
- Obtain blood samples for:
 - Hematology
 - Chemistry
 - HCV RNA
 - Viral sequencing/phenotyping
 - HIV-1 RNA and CD4 cell count will only be collected and analyzed for HIV co-infected subjects
 - HBV DNA (only in subjects who are HBcAb+ at Screening)
 - Serum β -hCG pregnancy test for females of childbearing potential only

6.4.2. Posttreatment Week 12 Visit (\pm 5 days): Group 1, Group 2 and Group 3

The following procedures/assessments are to be completed at Posttreatment Week 12 and 24:

- Perform complete physical examination, including vital signs
- Assessment of SAEs
- Subject completes Health Related Quality of Life Questionnaire: SF-36, CLDQ-HCV, FACIT-F, and WPAI
- Obtain blood samples for:
 - Hematology
 - Chemistry
 - HCV RNA
 - HBV DNA (only in subjects who are HBcAb+ at Screening)
 - Viral sequencing/phenotyping

6.4.3. Posttreatment Week 24 Visit (\pm 5 Days): Only for Subjects who Achieved SVR12

The following procedures/assessments are to be completed at Posttreatment Week 24:

- Perform complete physical examination, including vital signs
- Assessment of SAEs
- Obtain blood samples for:
 - Hematology
 - Chemistry
 - HCV RNA
 - HBV DNA (only in subjects who are HBcAb+ at Screening)
 - Viral sequencing/phenotyping

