6.5. Early Termination (ET)

For subjects who have completed an ET visit, the posttreatment Week 4 and 12 follow-up visits will be scheduled after last dose of any of the study drug. Subjects who achieve SVR12 (HCV RNA < LLOQ at posttreatment Week 12) will complete the posttreatment Week 24 visit.

When medically feasible, the medical monitor must be consulted prior to subject discontinuation. If a subject discontinues study dosing (for example, as a result of an AE), every attempt should be made to keep the subject in the study and continue to perform the required study-related follow-up and procedures (see Section 3.4, Criteria for Discontinuation of Study Treatment). If this is not possible or acceptable to the subject or investigator, the subject may be withdrawn from the study.

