7.2.2. Adverse Events

Following initiation of study medication, collect all AEs, regardless of cause or relationship, until 30-days after last administration of study IMP and report to the CRF/eCRF database as instructed.

All AEs should be followed up until resolution or until the adverse event is stable, if possible. Gilead Sciences may request that certain AEs be followed beyond the protocol defined follow up period.

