8.6.2. Adverse Events

Clinical and laboratory adverse events will be coded using the Medical Dictionary for Regulatory Activities (MedDRA). System Organ Class (SOC), High-Level Group Term (HLGT), High-Level Term (HLT), Preferred Term (PT), and Lower-Level Term (LLT) will be attached to the clinical database.

Events will be summarized on the basis of the date of onset for the event. A treatment-emergent adverse event will be defined as any adverse event that begins on or after the date of first dose of study drug up to the date of last dose of study drug plus 30 days.

Summaries (number and percentage of subjects) of treatment-emergent adverse events (by SOC, and PT) will be provided by treatment group:

- All AEs
- AEs of Grade 3 or above
- AEs of Grade 2 or above
- All treatment-related AEs
- Treatment-related AEs of Grade 3 or above
- Treatment-related AEs of Grade 2 or above
- All SAEs
- All treatment-related SAEs
- All AEs leading to premature discontinuation of the study drug
- All AEs leading to temporary interruption of the study drug

All AEs collected during the study will be presented in the data listings.

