#### 7.1.5. Treatment-Emergent Adverse Events

##### 7.1.5.1. Definition of Treatment-Emergent

Treatment-emergent adverse events (TEAEs) are defined as one or both of the following:

- Any AEs with an onset date on or after the study drug start date and no later than 30 days after permanent discontinuation of study drug.
- Any AEs leading to premature discontinuation of study drug.

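### When posttreatment Week 4 is held before day 30, no scheduled contact collects non-serious AEs for the last 1 to 7 days of the 30-day window, and the schedule then limits the next visit to SAEs

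*Protocol*

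**What the plan says.** **Collection and analysis window.** Protocol 7.2.2 requires sites to "collect all AEs, regardless of cause or relationship, until 30-days after last administration of study IMP". Protocol 8.6.2 counts an AE as treatment-emergent if it begins "up to the date of last dose of study drug plus 30 days", and SAP 7.1.5.1 uses onset "no later than 30 days after permanent discontinuation of study drug". Protocol 5.4 sets the same end for recording concomitant medications: "up to and including 30 days after the last dose of study drug".

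**Visits.** Protocol 6.4.1 assesses all AEs and concomitant medications at posttreatment Week 4, with a ±5-day allowance. At posttreatment Weeks 12 and 24, sections 6.4.2 and 6.4.3 list only "Assessment of SAEs". Footnote b of Appendix Tables 1 to 3, repeated in the SAP's copies, says the same: "Only SAEs will be collected at post-treatment Weeks 12 and 24". The concomitant medication row of the tables stops at posttreatment Week 4.

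**Other relevant text.** The synopsis lists AEs and concomitant medications among the posttreatment assessments without restricting the later visits to SAEs. Protocol 9.1.6 limits the eCRF casebook to data that the schedule of events and procedures calls for. Protocol 6.6 has AEs and medications collected at unscheduled visits, which take place only if the sponsor or investigator asks for one.

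**The concern.** The AE tables will be read as covering last dose + 30 days in every subject. For a subject seen before day 30, the schedule gives the site no later point at which to ask about the remaining days, and it restricts the next visit to SAEs. Suppose a subject mentions at Week 12 a non-serious event that began on day 29, the day after a Week 4 visit on day 28. Section 7.2.2 says to record it; footnote b says not to.

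Safety and tolerability is a primary objective, and protocol 1.5 names high exposure to the main sofosbuvir metabolite as a concern in this population. Any events lost this way lower the reported incidence, and how many are lost depends on attendance dates rather than on the drug.

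**Working it through.** The plan states no figure for this coverage, so there is none to reproduce. The check is day arithmetic.

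**Inputs**
- End of the AE window: day 30 after last dose (Protocol 7.2.2 and 8.6.2; SAP 7.1.5.1).
- Posttreatment Week 4: nominal day 28 (SAP Table 3-2), ±5 days (Protocol 6.4.1 and Appendix 2).
- Day count: SAP 3.6.2 counts follow-up days from the last dose date. Protocol 6.5 says of early terminators that "the posttreatment Week 4 and 12 follow-up visits will be scheduled after last dose of any of the study drug". I assume the same origin for subjects who complete treatment.
- Planned treatment: 56, 84 and 168 days (SAP 4.2.2).

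**Permitted visit days**
- Week 4: 28 − 5 = 23 to 28 + 5 = 33, which is 11 days.
- Week 12: 84 − 5 = 79 to 84 + 5 = 89.

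**Uncovered days = max(0, 30 − visit day)**, taking the visit day itself as covered:

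| Visit day | 23 | 24 | 25 | 26 | 27 | 28 | 29 | 30–33 |
|---|---|---|---|---|---|---|---|---|
| Uncovered days | 7 | 6 | 5 | 4 | 3 | 2 | 1 | 0 |

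A gap arises on 7 of the 11 permitted days. If visits were spread evenly over the window (an assumption), the mean gap would be (7+6+5+4+3+2+1)/11 = 28/11 = 2.5 days.

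**Share of the 30 posttreatment days:** 2/30 = 6.7% at the nominal day; 7/30 = 23.3% at most.

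**Share of the whole treatment-emergent window (planned treatment days + 30):**

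| Group | Window | Visit on day 28 | Visit on day 23 |
|---|---|---|---|
| 1 (8 weeks) | 56 + 30 = 86 days | 2/86 = 2.3% | 7/86 = 8.1% |
| 2 (12 weeks) | 84 + 30 = 114 days | 2/114 = 1.8% | 7/114 = 6.1% |
| 3 (24 weeks) | 168 + 30 = 198 days | 2/198 = 1.0% | 7/198 = 3.5% |

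**What the gap reaches**
- SAEs: not affected. Protocol 7.2.3 collects them throughout follow-up.
- Deaths: not affected. SAP 7.1.6 summarises all of them, treatment-emergent or not.
- Primary safety endpoint (AEs that cause study drug to be stopped for good): not affected. An event that starts 24 to 30 days after the last dose cannot cause stopping.
- Concomitant medication summary: not affected. SAP 7.4 already leaves out medications started after the last dose, so only the by-subject listing could be incomplete.
- Non-serious AEs with onset after the Week 4 visit and by day 30: affected.

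**The case against.** The best defence is that 7.2.2 is a standing duty, not tied to any visit. A site may learn of a day-29 event by other means and record it, unscheduled visits take AEs, and the eCRF completion guidelines, which are not among these documents, may say how. Visits on days 30 to 33 leave no gap at all. This stands, and it rules out a stronger reading that a reader might infer: that the end of the window goes unascertained in the trial as a whole. The documents show only that no scheduled contact covers it when Week 4 falls on days 23 to 29. The defence does not remove the conflict, because footnote b does more than omit a contact: it tells sites to take SAEs only at the next visit, and 9.1.6 ties the eCRF to the schedule.

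The second defence is that the consequence is small. The main named risk, a fall in red cells, is followed by scheduled hematology at posttreatment Weeks 4, 12 and 24. SAP 7.1.6 counts each subject once per summary, so a late event changes the overall any-AE count only in a subject with no earlier AE. The safety tables are descriptive and the trial has no control arm, so no between-arm comparison is biased. All of this stands. It also means that the percentages of days must not be read as percentages of AEs missed; the documents give no basis for estimating those.

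**Conclusion.** The point holds in limited form. For Week 4 visits on days 23 to 29, the last 1 to 7 days of the stated AE window have no scheduled collection of non-serious AEs, and 7.2.2 conflicts with 6.4.2 and footnote b. A subject seen exactly on the nominal day still has 2 uncovered days. The upper figures need every subject in a group to attend on the earliest permitted day, and all the shares assume full planned treatment and a day count from last dose.

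The result is a possible small downward bias in late non-serious treatment-emergent AEs. A reader might infer that the primary safety endpoint or the concomitant medication tables are compromised; the definitions in Protocol 8.1.2 and SAP 7.4 do not support that. The correction is worth making because it is cheap and makes the AE tables match their stated window.

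A separate contradiction concerns the last pregnancy test. Protocol 6.9.15 places it 30 days after last dose or at the last study visit, whichever is later. Appendix 4 and the schedule tables end testing at posttreatment Week 4, which can fall on day 23. These passages must be reconciled. They have no bearing on the AE argument.

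**What to change.** Amend footnote b in Protocol Appendix Tables 1 to 3 and in the SAP's copies, and amend Protocol 6.4.2, so that posttreatment Week 12 records:
- SAEs, as now;
- any non-serious AE not yet recorded whose onset was on or before last dose + 30 days;
- any concomitant medication from that period not yet recorded, for the record that 5.4 requires.

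The concomitant medication row needs a matching entry at Week 12. The cost is six footnotes, one section, the medication rows and one extra question at a visit that already takes place. The drawback is recall. An event on day 30 asked about on day 79 is 49 days old (7 weeks), and one on day 24 asked about on day 89 is 65 days old (about 9 weeks), so some minor events will be forgotten.

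A telephone contact on days 30 to 33 for subjects seen before day 30 would shorten recall but adds a contact. Moving the Week 4 visit to days 30 to 33 is less attractive: SAP Table 3-2 summarises follow-up laboratory and vital sign data only to day 30, so day 30 alone would serve both purposes.

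Separately, reconcile 6.9.15 with Appendix 4 and the pregnancy test rows.
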